test at screening and on the day before dosing and must use medically acceptable methods of birth control. Acceptable methods of birth control include oral or transdermal contraceptives, condoms, spermicidal foam, IUD, progestin implant or injection, abstinence, vaginal ring, or sterilization of partner. The reason for non-childbearing potential, such as bilateral tubal ligation, bilateral oophorectomy, hysterectomy, or post-menopausal for ≥ 1 year, must be specified in the patient's medical history file and CRF.

• Must have adequate organ and immune function as indicated by the following laboratory values:

Parameter Laboratory ValuesSerum creatinine≤1.5 x ULN

Est. creatinine clearance ≥45 mL/min							
Total bilirubin	\leq 2.0 mg/dL (\leq 34.2 µmol/L)						
AST & ALT	≤3 x ULN						
Absolute granulocytes	$\geq 1.5 \text{ x } 10^9 \text{ cells/L}$						
Platelets >	100,000/µL						

• Be able to read orunderstand, and provide a signature or thumb impression on the Informed Consent Form (ICF) before entering the study.

Exclusion Criteria

- Subject has not failed at least one courses of non-MTX chemotherapy or one course of non-MTX chemotherapy and chemo radiation for treating their SCCHN.
- Uncontrolled active infection.
- Current mucositis (>Grade 1).
- Pregnant or nursing mother.
- Prior history of a cerebrovascular accident or hemorrhage.
- Congestive heart failure, as defined by New York Heart Association class III or IV.
- Uncontrolled hypertension.
- Active psychiatric/mental illness making informed consent or useful clinical follow-up unlikely.
- Subjects who have previously been enrolled into this study and subsequently withdrew.
- Subject receiving other investigational agent(s).
- Any systemic immunosuppressive medication/therapy (eg, other chemotherapy, steroids).
- Any significant systemic illness, unstable or severe medical condition(s) that could put the subject at risk during the study, interfere with outcome measures, or affect compliance with the protocol procedures such as intercurrent infection and/or autoimmune disease, ie, any condition that compromises the immune system.
- Known or suspected intolerance or hypersensitivity to the study materials (TK-112690 and/or excipients or closely related compounds).
- Subjects, who have received, or plan to receive, radiation or chemotherapy within 4 weeks of screening.
- Subjects that have a history of poor compliance in clinical research studies.
- Subjects that have participated in any other investigative clinical trial in the past 4 weeks.

Dose and Dosing Regimen

The dose of METREXASSISTTM (TK-112690) will be 45 mg/kg administered parenterally over one hour in a clear, neutral, aqueous formulation (no organic chemical excipients). METREXASSISTTM will be given one hour before and 5 hours after the MTX treatment. The nutrient drink will be given one hour before METREXASSISTTM infusion. The MTX formulation will that traditionally used as standard-of-

care at a study site.

Test Product, Dose and Mode of Administration

- METREXASSISTTM (TK-112690 for Infusion) is a clear, sterile, neutral (pH=7.4), aqueous solution containing 5 mL of 100 mg/mL TK-112690.
- METREXASSISTTM is packaged as a 5 mL solution in a 10 mL flint glass vial with an elastomeric stopper held in place by an aluminum seal and flip-off cap. The concentration of TK-112690 in the solution is 100 mg/mL
- METREXASSISTTM will be administered as a continuous iv infusion over a duration of one hour in a volume of 250 mL normal saline.
- The nutrient drink, Fortasyn Connect[™] / Souvenaid[™], is commercially available as a 125 mL, 125 kcal solution. The drink is administered orally.
- The placebo is isotonic saline.

Reference Therapy or Comparator

Placebo-Isotonic saline

Follow-up

[figure not shown]
Subjects need to return at Day 1 of Week 6, which is two weeks from the last dose of the study drug.

Statistical Methods

- Safety: AEs, vital signs, physical examination data and clinical laboratory data will be analyzed using descriptive statistics with safety outcomes for patients in a dose group pooled & compared with patients in other groups.
- Mucositis: Scale data from individual doses groups will be analyzed using descriptive statistics.
- Surrogate Markers: Plasma concentration data evaluated for individual doses groups using descriptive statistics as well as compared with Surrogate marker data from the completed Phase 1bstudy.

INTRODUCTION

Methotrexate (MTX, structure below) was introduced in the early 1950s and remains the main antifolate in widespread use despite numerous attempts to replace or complement this chemotherapeutic.^{1,2,3,4}MTX is used to treat a variety of cancers, such as head and neck cancer, leukemia, osteosarcoma, breast cancer, acute lymphoblastic, lymphocytic/meningeal leukemia, and non-Hodgkin lymphoma. It is also used to treat cancer of the uterus, breast, lung, gestational choriocarcinoma, chorioadenoma destruens, and hydatidiform mole. In these applications, MTX limits the metabolism of the cancer cell by inhibiting the enzyme responsible for folic acid metabolism, resulting in cellular folic acid deficiency, causingcell death. A particularly attractive application of MTX is as a relatively inexpensive, but useful, palliative treatment for advanced head and neck cancer.⁵

MTX is also used clinically in a variety of other pathogenic conditions, including rheumatoid arthritis, psoriasis, uveitis, and graft-versus-host disease.⁶ In these applications, lower doses of MTX are used and the effect is generally attributed to an immunosuppression phenomenon.

Besides affecting cancerous tissue, MTX often produces unintended adverse effects in normal, non-cancerous, tissues, particularly tissues that have a high rate of proliferation, such as gut and bone marrow.⁷ The side effects of MTX can threaten survival. Gastrointestinal mucosa, bone marrow, liver and hair are particularly vulnerable to the effects of MTX. Renal toxicity is also frequent with high doses of MTX.

¹Mager DR, Methotrexate, Home Health Now. 2015; 33:139-41.

² McGuire JJ. Anticancer antifolates: Current status and future directions. Curr Pharm Des. 2003; 9:2593-613.

³ Visentin M, Zhao R, Goldman ID. The antifolates. Hematol Oncol Clin North Am. 2012; 26:629-48.

⁴ Jolivet J, Cowan KW, Curt GA, Clendeninn NJ, Chabner BA. The pharmacology and clinical use of MTX. N Engl J Med. 1983; 309:1094–1104.

⁵ Chakraborty S, Geetha M, Sujith KM, Biji MS, Sateeshan B. Palliative low dose fortnightly methotrexate in oral cancers: Experience at a rural cancer centre from India. South Asian J Cancer. 2014; 3:166-170.

⁶Hashkes PJ, Becker ML, Cabral DA, Laxer RM, Paller AS, Rabinovich CE, Turner D, Zulian F.

Methotrexate: new uses for an old drug. J Pediatr. 2014; 164: 231-6.

⁷Gaies E, Jebabli N, Trabelsi S, Salouage I, Charfi R, Lakhal M, Klouz A, Methotrexate Side Effects: Review Article. J Drug MetabToxicol 2012. 3:125-129.

Mucositis describes the inflammation, lesions, and ulcers that develop in the oral and gastrointestinal tract because of treatment with chemotherapeutics such as MTX.⁸ An effective adjuvant treatment that ameliorates MTX-induced mucositis would provide important relief to cancer patients undergoing chemotherapy.

Mucositis can affect up to 100% of people receiving high doses of chemotherapy.⁹ The frequency of mucositis is responsible for increased patient hospitalization, resulting in a substantial financial burden for both patients and hospitals^{10,11} In addition, mucosal damage increases the susceptibility of infection and sepsis in neutropenic patients. Pain, discomfort and the inability to eat or drink are the most frequent occurrences for patients undergoing chemotherapy. As a result, delays and suspensions in chemotherapy regimens are common for patients experiencing severe mucositis. The frequency, financial burden, and disruptions of effective cancer therapy all underscore the need for treatments that can mitigate mucositis.

To date, no product is available to effectively treat MTX-induced mucositis, especially mucositis outside the oral cavity:

Several publications from animal studies have revealed evidence for compounds that can protect against MTX induced small intestinal damage. These potentially therapeutic compounds include various nutraceuticals, α-lipoic acid, lactoferrin, taurine, docosahexaenoic acid, prostaglandin E₁, N-acetylcysteine.^{12,13,14,15,16[,17,18]} To date, none of these compounds are being widely explored in the clinic as potential side-effect reducing adjuvants for MTX-induced mucositis.

⁸ Villa A, Sonis ST. Mucositis: pathobiology and management. CurrOpin Oncol. 2015; 27:159-64.

⁹ Sonis ST, Perspectives on Cancer Therapy-Induced Mucosal Injury. Cancer. 2004;100:1995-2025.

¹⁰ Carlotto A, Hogsett VL, Maiorini EM, Razulis JG, Sonis ST. The economic burden of toxicities associated with cancer treatment: review of the literature and analysis of nausea and vomiting, diarrhoea, oral mucositis and fatigue. Pharmacoeconomics. 2013; 31: 753-66.

¹¹Elting, LS, The Burdens of Cancer Therapy. Cancer. 2003;98:1531-1539.

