- Study follow-up will occur on Week 6, two weeks after the last dosing of MTX.
- Blinding: The study will be partially blinded. The patient and investigator will be blinded as to whether TK-112690 or placebo is administered. The CRO,sponsor, and site pharmacist will know whether the patient was administered active drug or placebo.

Main Study Endpoints/Outcomes

• Mucositis Outcomes

Mucositis status in the patients will be evaluated using 4 different published and validated mucosit scales: OMAS/Sonis, PROMS, WHO, and CTCAE/mucositis.

• Surrogate Marker Outcomes

Plasma samples will be obtained to determine surrogate markers of mucositis, eg, CD40/CD40. TNF- α , etc.

• Safety Outcomes

Adverse events will be assessed throughout the study. Incidents of toxicity will be determined to at least possibly related to the study drug and graded according to CTCAE Version 4.0.

Study Procedures and Study Assessments

- A review of a patient's medical history including a detailed history of the patient's cancer and concomitant medications will be performed at screening.
- Screening for drugs of abuse will be performed at the time of patient screening and Day 0 (the day before start of study).
- Vital sign measurements will be performed at patient screening, on Day 0, and at 24 and 48

hours post each initial infusion of TK-112690/placebo as well as on Day 1 of Week 6.

- Physical examinations will be performed at screening, on Day 0, and 24 and 48 hours post each initial infusion of TK-112690/ placebo as well as on Day 1 of Week 6.
- ECOG performance status will be determined at patient screening, on Day 0, and at Day 1 of Weeks 6.
- For pre-menopausal females, a urine pregnancy test will be performed at screening, on Day 0, and at Day 1 of Week 6.
- 12-Lead ECG at screening and 24 hours post each initial infusion of TK-112690/ Placebo.
- CBC, Liver function test, Kidney function test determination at the clinical site prior to methotrexate treatment to ensure patient fit to dose.
- Serum chemistry, hematology, coagulation and urinalysis at screening, Day 0, and at 24 and 48 hours post each initial infusion of TK-112690/ placebo as well as on Day 1 of Week 6.
- Adverse events will be evaluated 5, 24 and 48 hours post each initial infusion of TK-112690/ Placebo as well as on Day 1 of Week 6.

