METREXASSISTTM, TK-112690 for parenteral use, is a novel, non-toxic and specific therapy to treat mucositis caused by MTX treatment. In mouse models of human MTX-induced mucositis, TK-112690 protects from weight loss, one of the cardinal features of human mucositis, as well as limits the increase in systemic WBC concentration and mucosal permeability observed in mice post-MTX treatment. TK-112690 does not affect the cytotoxicity of MTX toward cancer cellsin*in vitro* and *in vivo* studies. Various other preclinical studies and a single dose study in human volunteers suggest no safety concerns with TK-112690.

The protocol provided in this document was designed further determine the tolerability of TK-112690 when administered weekly along with MTX as an intravenous infusion in patients with local, advanced, recurrent, metastatic SCCHN. Relevant mucositis endpoints will also be collected in the study. To increase the reliability of the results, the study is partially blinded- The patient and investigator will be blinded as to whether TK-112690 or placebo is administered onlythe CRO, sponsor and site pharmacist will know whether the patient was administered active drug or placebo.

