1.2. SUMMARY PRE-CLINICAL EFFICACY RESULTS

In animal models of the human condition of mucositis, TK-112690 protects from three cardinal features associated with MTX-induced mucositis: weight loss, WBC increase (likely caused by infection), and increased mucosal permeability. The efficacy of TK-112690 in the weight loss model parallels the elevation in plasma uridine induced by inhibition of uridine phosphorylase. Findings in three *in vitro* studies and two *in vivo* studies with MTX and TK-112690 in human cancer cells suggest no effect of TK-112690 on the chemotherapeutic effect of MTX. Overall, the efficacy data suggest that treatment with TK-112690 may provide an innovative and useful approach to MTX-associated mucositis in man.

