1.5.1.11 Overall Summary

The findings above suggest:

- No safety concerns are apparent.
- Variability in blood levels for TK-112690 is modest, $\leq 25\%$.
- The MRT for TK-112690 is consistent with bid dosing.
- The AUC_{0-24h} for TK-112690 at a 25 mg/kg dose of TK-112690, approximately 200 μg* h/mL, is more than twice that needed to achieve efficacy in the MTX-induced weight loss model, 80 μg* h/mL, (Figure 1, bid dosing).

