6.5. VITAL SIGNS, WEIGHT DETERMINATIONS AND CARDIOVASCULAR ASSESSMENTS

Body temperature will be recorded by the oral, rectal or tympanic route at screening and during weekly visits. The same route should be used for all measurements, if possiblesupine blood pressure (systolic and diastolic), respiratory rate and pulse will be recorded at screening (defined as baseline) and at Day 0, and 24 and 48 hours post TK-112690 /placebo infusions as well as on Day 1 of Week6. The time of the measurements will be noted. All measurements will be made with the subject in the supine position. Blood pressure should be determined by cuff (manual or automated is acceptable, although the same method should be used throughout the study).

Weight will be determined concurrent with vital sign measurements.

A standard 12 lead ECG will be recorded at screening (defined as baseline) and at 24 post each TK-112690/placebo dosing. The PI will provide an overall judgment of the ECG.

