7.1.1 Screening Visit

To be accomplished within 15 days of expected initial dosing and ONLY AFTER THE ICF IS SIGNED.

An Eligibility Screening Form (ESF) documenting the subject's fulfillment of the entry criteria for all subjects considered for the study is to be completed by the PI. Subjects who are considered for study entry, but who fail to meet the eligibility requirements, will also have an ESF completed with the reason for ineligibility. These subjects will not be entered into the trial database. The ESFs for subjects who fail to meet the eligibility criteria requirements should be kept in the files at the sites.

During this visit the following activities will be performed:

- Eligible subjects meeting the inclusion/exclusion criteria for this study will be asked to read, comprehend, and sign/thumb impression an informed consent form.
- The subject medical history and concomitant medication use will be recorded as well as a history of drug abuse, alcohol consumption, and tobacco use.
- Perform a urine screen for drugs of abuse.
- A complete physical examination will be performed assessing the following: Skin, eyes, ear, nose, throat, neck, thyroid, lungs, heart, abdomen, lymph nodes, extremities, and body weight.
- Vital signs and weight will be measured as well as an AE assessment.
- ECOG performance status (Section 20.2 Appendix 2)
- A pregnancy test will be performed on women of childbearing potential.
- A 12-lead ECG will be performed.
- The following laboratory test will be performed: hematological panel, infective agent panel, serum chemistry, coagulation and urinalysis (Laboratory tests, see **Table 10** for complete list of tests).
- Disease (tumor) assessment by CT scanning will be performed within 7 days post screening but before the first dosing.

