10.3. ANALYSIS OF SAFETY

Subjects in study will be evaluated for safety at Week 1 and 2. Subjects with tolerable toxicity will be allowed to continue study therapy for an additional 2 weekly treatments and possibly more at the discretion of the investigator.

Vital signs (systolic and diastolic blood pressure, and pulse), weight determinations and physical examination results will be summarized by treatment group using appropriate descriptive statistics. Continuous variables will be summarized using the number of observations, mean, standard deviation, minimum, median and maximum values. Categorical values will be summarized using number of observations and percentages.

Withdrawals from the study will be summarized by dose group.

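### Body weight, called a cardinal feature of mucositis and collected 11 times in both arms, is planned only as a raw-value safety summary, with no change from Day 0 and no supportive efficacy role

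*Combined protocol and SAP*

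**What the plan says.** **Efficacy.** The synopsis (Main Study Endpoints/Outcomes) states: "Mucositis status in the patients will be evaluated using 4 different published and validated mucosit scales: OMAS/Sonis, PROMS, WHO, and CTCAE/mucositis". Section 3.1 likewise defines efficacy by scores on four scales. Weight is in neither the efficacy list nor the PD list.

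**Standing given to weight.** The Rationale for the Clinical Development of TK-112690 says that in mouse models "TK-112690 protects from weight loss, one of the cardinal features of human mucositis". Section 1.2 puts it first of three: "TK-112690 protects from three cardinal features associated with MTX-induced mucositis: weight loss, WBC increase (likely caused by infection), and increased mucosal permeability". Section 1.3.2 reports dose-ranging efficacy in the weight-loss model. Section 1.5.1.11 judges human exposure against the same model: the AUC at 25 mg/kg "is more than twice that needed to achieve efficacy in the MTX-induced weight loss model".

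**Collection.** Section 6.5: "Weight will be determined concurrent with vital sign measurements". Sections 7.1.1 to 7.1.4 and Table 12 place weight at screening, Day 0, 24 h and 48 h in each of Weeks 1 to 4, and Week 6. Section 8.2 adds a weight at early withdrawal.

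**Analysis.** The only planned use is in Section 10.3, Analysis of Safety: "weight determinations and physical examination results will be summarized by treatment group using appropriate descriptive statistics". For continuous variables that section names the number of observations, mean, SD, minimum, median and maximum. It names no change from baseline, percent loss or arm difference for weight.

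**The concern.** Patients differ much more from one another in body size than one patient is likely to change in a few weeks. A by-visit summary of raw weights carries all of that between-patient spread. It also describes a different set of patients at each visit as people leave. Change from each patient's own Day 0 value removes body size and keeps each patient as their own reference.

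Weight would complement the scales. The Introduction stresses the unmet need for mucositis outside the oral cavity, whereas the scales in Appendix 6 score the mouth, oral symptoms and oral intake. Section 1.5.2.14 reports that many Phase 1b scale values were low. Section 10.1.1 expects the trial at least to supply the data needed to power the next study. An SD of weight change would serve that purpose, and a raw-weight SD would not. If the analysis is left unspecified, it can still be done later, but then as a post hoc choice by a sponsor and CRO that know the assignments (Section 3.5).

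**Working it through.** The plan has no figure to reproduce: Section 10.1.1 says the sample size does not come from a statistical calculation.

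**1. Number of weights per patient.** Screening 1 + Day 0 1 + (2 per week × 4 weeks) 8 + Week 6 1 = 11. Cross-check: the laboratory tests follow the same visits, and Table 11 gives 154 mL / 14 mL = 11 draws.

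**2. Between-patient spread.** No weight SD is given. The nearest figure is Phase 1b Week 0 BMI in Table 9, as mean/SD/n by dose: 18/2/3, 20/5/3, 17/2/4, 19/4/15.

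- Mean = (18×3 + 20×3 + 17×4 + 19×15)/25 = 467/25 = 18.68 kg/m²
- Pooled SD = √[(2×2² + 2×5² + 3×2² + 14×4²)/21] = √(294/21) = 3.74 kg/m²
- CV = 3.74/18.68 = 20.0%

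BMI already adjusts for height, so raw weight is assumed to vary at least about as much.

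**3. 95% half-width for an arm difference.** Half-width = t(0.975; 2n−2) × SD × √(2/n).

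- n = 11 per arm: 2.086 × √(2/11) = 0.889 × SD. Raw BMI: 0.889 × 3.74 = 3.33 kg/m², or 17.8% of the mean.
- n = 7 per arm: 2.179 × √(2/7) = 1.165 × SD. Seven comes from Phase 1b completion (Section 1.5.2): 14 of 19 men plus 2 of 6 women = 16 of 25 = 64%, and 0.64 × 11 = 7.0.

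**4. Assumed SD of percent change.** With within-patient correlation r, SD of change ≈ CV × √[2(1−r)], taking change relative to the group mean. The documents give no r.

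| Quantity | SD | Implied r | ± at 11 per arm | ± at 7 per arm |
|---|---|---|---|---|
| Raw value, % of mean | 20.0% | – | 17.8 | 23.3 |
| % change from Day 0 | 2% | 0.995 | 1.8 | 2.3 |
| % change from Day 0 | 3% | 0.989 | 2.7 | 3.5 |
| % change from Day 0 | 5% | 0.969 | 4.4 | 5.8 |
| % change from Day 0 | 9% | 0.90 | 8.0 | 10.5 |

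At the cautious end (SD 9%) the interval is still less than half the raw one. By the formula, the ranking reverses only if r falls below 0.5.

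**5. Shifting denominators.** In Table 9 the BMI counts fall from 15 to 10 (60 mg/kg) and from 4 to 2 (45 mg/kg) between Week 0 and Week 4. Raw visit means in Phase 1b therefore compare different patients over time.

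**The case against.** The strongest reply is that this is an optional extra. Much of it stands.

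- **A reader might infer that an efficacy signal is lost.** The documents do not support that. Every weight is recorded, change can be derived at any time, and the wording of Section 10.3 does not exclude it. What is missing is pre-specification.
- **A reader might infer that the trial lacks any objective measure.** It does not. Plasma markers such as CD40/CD40L are outcomes, with 17 samples per patient (Section 6.7.3), although Section 1.5.2.13 found them highly variable. The synopsis also has opioid use assessed. Eating and drinking already enter the WHO, CTCAE and PROMS scales.
- **A reader might set low power on raw weights against near-certain power on change.** No between-arm test is planned for any outcome, the scales are also descriptive, and no size of weight effect is given. Power for a 5% difference, taking raw BMI SD 4 and mean 19, is 22% to 76% on change for r from 0.90 to 0.98, so such a contrast mostly reflects its assumptions. Interval width is the fair comparison.
- **A reader might take weight as the foundation of the animal case.** It is one of three features, beside WBC and permeability.
- **A human weight effect is unproven.** Phase 1b mean BMI was 18/20/17/19 at Week 0 and again at Week 4. Those are rounded means with dropout, and every patient received TK-112690, so they do not show what placebo patients would do. They also give no support for any particular arm difference.

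None of this favours raw values over change. Weight is non-specific in advanced SCCHN, which limits it to a supportive role.

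**Conclusion.** The point holds as a cheap improvement to the analysis plan. Weight is collected at 11 scheduled times in both arms, and its only stated use is a safety summary of raw values. At 11 per arm the 95% interval for a raw difference is about ±18% of the mean. For percent change from Day 0 it is about ±1.8 to ±8 points, or about ±2.3 to ±10.5 points with 7 completers per arm.

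This rests on Phase 1b BMI as a proxy for weight and on an assumed SD of change of 2% to 9%. The documents give neither an SD of change nor an effect size. The figures show that change is the more precise summary; they do not show that the trial would detect an effect on weight.

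**What to change.** 1. In Section 10.3, summarise weight by arm as percent change from Day 0 at each visit, alongside the raw values.
2. In the synopsis outcomes and Section 3.1, name the arm difference in percent change, with a 95% interval, at Week 4 (48 h) and Week 6. Label it supportive, descriptive and not the lead outcome.
3. State that Day 0 is the weight baseline. Section 6.5 treats screening as baseline for vital signs, with which weight is taken, and screening may be up to 15 days earlier.
4. Show withdrawal weights separately or as a sensitivity analysis. Mixing them with Week 4 values would combine different follow-up times, and Section 8.2 lists disease progression as a reason for withdrawal.
5. Name a population that covers both arms. Section 10.2.1 defines the safety population by receipt of TK-112690, which read literally leaves out placebo patients.

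**Cost:** wording only, with no new visits, measurements or patient burden. It adds two descriptive comparisons to a plan that already has four scales and no designated lead, hence the supportive label. Weight also changes with tumour progression and other causes of poor intake, so it cannot by itself be evidence on mucositis.

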- Blood samples will be obtained pre-initial infusion of TK-112690/ placebo and 5, 24 and 48 hours post each initial infusion as well as on Day 1 of Week 6. Plasma will be obtained from the blood samples in order to determine surrogate markers of mucositis, e.g., CD40/CD40L, TNF- α , etc.
- Patients will be evaluated for extent and severity of mucositis using established mucositis rating scales, e.g., OMAS/Sonis, PROMS, WHO, and CTCAE/mucositis on the day prior to study start (Day 0), and 24 and 48 hours post each initial infusion of TK-112690/ placebo as well as on Day 1 of Week 6. Examination will assess the lining of the mouth, throat, and other linings of the digestive tract. Incidence of oral mucositis, duration of severe oral mucositis, throat soreness, severity of pain and use of parenteral or transdermal opioid analgesics will be assessed.

Study Population

Patients at least 18 years old, diagnosed with locally advanced or residual or recurrent or metastatic SCCHN and scheduled to receive 45 mg/m² MTX to treat their cancer. The diagnosis must be confirmed by histopathology or cytology.

Inclusion Criteria

- Male and female subjects over 18 years old with a histologically or cytological confirmed diagnosis of locally residual, recurrent or metastatic SCCHN.
- Subject must have failed at least onecourses of non-MTX chemotherapy, orone course of non-MTX chemotherapyand chemo radiation for treating their SCCHN.
- No prior systemic treatments for cancer (chemotherapy and/or radiotherapy) 4 weeks prior to screening.
- No other concurrent, active, invasive malignancies.
- An Eastern Cooperative Oncology Group (ECOG) performance status of 0 to 2.
- Must have a life expectancy of at least 6 months.
- History of brain metastases allowed if disease has stabilized or improved after radiation and/or craniotomy.
- No active angina or uncontrolled arrhythmia.
- No detectable infection including hepatitis B/C and HIV.
- Not pregnant or nursing. Women of childbearing potential must have a negative urine pregnancy

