2.0. STUDY OBJECTIVES

2.1. PRIMARY OBJECTIVE

The primary objective of this study is to establish pilot efficacy compared to placebo for TK-112690 as an anti-mucositis agent when administered weekly for 4 weeks by iv infusion to subjects with locally advanced, residual or recurrent or metastatic SCCHN scheduled to receive MTX as chemotherapy.

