3.0. STUDY DESIGN AND TREATMENT

3.1 STUDY OUTCOMES/ENDPOINTS

Key study outcomes/endpoints are listed below:

- Efficacy. Mucositis scores in 4 standard mucositis scales.
- PD: Evaluation potential relationships among TK-112690 dose, mucositis scores, and surrogate markers of mucositis, e.g., CD40/CD40Land TNF-α.

[figure not shown]

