10.2. POPULATIONS

10.2.1. Efficacy and Safety Population

The efficacy population will consist of all subjects who received at least four doses of TK-112690. The safety population will consist of all subjects who receive at least one dose of TK-112690.

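### As worded, both analysis populations omit the placebo arm; the four-dose rule also selects after randomisation, no between-arm estimate is named, and 11 per arm cannot size the next study accurately

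*Combined protocol and SAP*

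**What the plan says.** Section 2.1: "The primary objective of this study is to establish pilot efficacy compared to placebo for TK-112690 as an anti-mucositis agent". The endpoint in Section 3.1 is "Efficacy. Mucositis scores in 4 standard mucositis scales", with no scale, time or summary placed first. The Synopsis (Study Procedures and Study Assessments) schedules scoring at 24 and 48 hours in each of four weeks and at Week 6. It also lists "Incidence of oral mucositis, duration of severe oral mucositis, throat soreness, severity of pain and use of parenteral or transdermal opioid analgesics", again unranked.

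The only analysis stated for these data is in the Synopsis, Statistical Methods: "Mucositis: Scale data from individual doses groups will be analyzed using descriptive statistics". Section 10 has safety subsections but no efficacy analysis.

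Section 10.2.1 sets the populations: "The efficacy population will consist of all subjects who received at least four doses of TK-112690" and "The safety population will consist of all subjects who receive at least one dose of TK-112690". Section 10.3, by contrast, says that safety data "will be summarized by treatment group using appropriate descriptive statistics".

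Section 10.1.1 states that the study is exploratory, that it may lack power and that its size does not come from a calculation. It then suggests that the difference might still reach significance, and says the least the study will deliver is enough data to power the next one accurately. Section 3.5 gives the CRO, sponsor and site pharmacist knowledge of the allocation, and provides a second randomisation list for 8 possible extra subjects.

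**The concern.** A comparison with placebo needs a population that contains placebo patients, a rule for membership that does not depend on what happens after randomisation, and a stated quantity to estimate. The plan as written supplies none of the three.

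The four-dose threshold matters even when it is applied to both arms. Patients who stop early for toxicity, progression or mucositis drop out of the efficacy set. If the reasons for stopping differ by arm, the remaining groups are no longer the randomised ones.

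Without a lead measure, there are 4 scales x 9 post-baseline times (2 x 4 weeks + Week 6) = 36 scale-by-time results, plus the further outcomes. People who know the allocation could choose among them once results by arm are visible.

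Finally, if the next trial is sized on these results as though they were accurate, it could be substantially too small or too large.

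**Working it through.** **No plan figure to reproduce.** Section 10.1.1 gives no alpha, power, effect or SD behind the 22 patients. The check is therefore of precision, in SD units, which needs no SD from the documents.

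**Populations, side by side.**
- Section 10.2.1 mentions TK-112690 only, in both definitions.
- Section 3.5 describes TK-112690 treatments made up with either active drug or placebo. Section 5.2 refers to a combined TK-112690/placebo dose. Sections 10.3 and 10.3.1 summarise safety by treatment group. The intention is evidently two arms, but none of these sections defines a population.

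**Meaning of four doses.**
- Section 7.1.3 gives two infusions at each weekly treatment, so four infusions are reached in Week 2 (2 x 2 = 4) and a full course is 2 x 4 = 8.
- The figure captions in Sections 1.5.2.11 and 1.5.2.12 use four completed doses to mean Study Weeks 1 to 4, that is, four weekly treatments.
- Section 1.5.2.1 calls the later infusion on the same day a second dose, which supports the first reading.

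**How many patients the rule might leave.** Table 9 gives Phase 1b BMI counts by week, summed over the 15, 30, 45 and 60 mg/kg cohorts:
- Week 0: 3 + 3 + 4 + 15 = 25
- Week 2: 3 + 3 + 3 + 14 = 23, so 11 x 23/25 = 10.1, about 10 per arm
- Week 4: 3 + 3 + 2 + 10 = 18, so 11 x 18/25 = 7.9, about 8 per arm

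These counts show presence at the visit, not confirmed dosing.

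**Precision.** With n per arm and df = 2n - 2:
- 95% half-width of a mean difference, in SDs: t(0.975, df) x sqrt(2/n)
- Sizing uncertainty from the SD alone: for a fixed raw difference, required N is proportional to SD squared, so the 95% limits of needed N divided by planned N are df/chi2(0.975, df) and df/chi2(0.025, df)

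| Case | n per arm | Half-width (SD) | Needed N / planned N |
|---|---|---|---|
| As planned | 11 | 2.086 x 0.426 = 0.89 | 20/34.17 to 20/9.59 = 0.59 to 2.09 |
| Extra 8 enrolled, equal split assumed | 15 | 2.048 x 0.365 = 0.75 | 28/44.46 to 28/15.31 = 0.63 to 1.83 |
| Four infusions required | 10 | 2.101 x 0.447 = 0.94 | 18/31.53 to 18/8.23 = 0.57 to 2.19 |
| Four weekly treatments required | 8 | 2.145 x 0.500 = 1.07 | 14/26.12 to 14/5.63 = 0.54 to 2.49 |

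The last column ignores uncertainty in the effect itself. As an illustration, an observed difference of 1.0 SD at 11 per arm has a 95% interval (noncentral t) of 0.10 to 1.88 SD.

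**The case against.** The strongest reply is that this is a declared pilot. Section 10.1.1 disclaims power, and descriptive analysis suits an exploratory study. That stands: 22 patients and an uncalculated sample size are not errors. It does not cover the sentence claiming accurate sizing, nor a population definition that omits the control arm.

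Several stronger readings are tempting but not supported.

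- A reader might infer that placebo patients will really be excluded and the comparison lost. Sections 3.5, 5.2, 10.3 and 10.3.1 point to a slip of wording, so the empty placebo arm follows from the drafting and is not a forecast.
- A reader might infer that no comparison by arm is planned at all. The Synopsis (Study Design) defines the two dose groups as TK-112690 treated and placebo treated, so descriptive summaries of each arm are already implied. What is missing is a named difference with an interval, and a ranking of measures.
- A reader might take Phase 1b completion, (14 + 2)/(19 + 6) = 16/25, and conclude that about 7 per arm would remain. That is completion of the whole trial, which had visits at 5 and 8 weeks (Section 1.5.2.1). The four-dose rule asks for less, and the weekly counts in Table 9 bear on it more directly.
- A reader might infer that the sponsor will pick its endpoint with the results in view. The documents show that the sponsor and CRO know the allocation. They do not say that anyone reviews mucositis scores by arm during the trial, and Section 10.5 rules out interim analyses. The opportunity is real; the act is not documented.

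**Conclusion.** The point holds and should be fixed before any data are reviewed by arm. Section 10.2.1 is wrong as written and, with the drug name corrected, would still select on exposure after randomisation under an ambiguous threshold. The primary objective has no lead measure and no named between-arm estimate.

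The accurate-sizing claim fails at 11 per arm and also at 15. Keeping the four-dose rule would widen the uncertainty further, to the 10 or 8 per arm rows of the table, depending on how a dose is read.

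The assumptions are a lead measure analysed as a mean difference with roughly normal data and equal SDs, a fixed raw difference for the sizing ratios, an equal split of the extra 8, and Phase 1b attendance as a stand-in for dosing here. The 45 mg/kg cohort in Phase 1b fell from 4 to 2, too few to give a rate specific to that dose.

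**What to change.** 1. **Section 10.2.1.** Define the efficacy population as all randomised subjects given at least one TK-112690 or placebo infusion, analysed as randomised. Define the safety population as all subjects given at least one TK-112690 or placebo infusion. Section 10.1.2 replaces anyone who leaves before completing first dosing, so state how a partly dosed patient who has been replaced is counted.
2. **New efficacy subsection in Section 10.** Before any review by arm, the sponsor names one lead scale and one summary of it, taking account of the Day 0 score because Section 4.3 lets Grade 1 mucositis in. Which scale leads is the sponsor's choice. Report the TK-112690 versus placebo difference with a 95% CI, and the other scales as supportive with no significance claims. Examine dropout in a sensitivity analysis that does not treat every exit as mucositis: Section 1.5.2.3 attributes all four Phase 1b discontinuations for adverse events to anemia. The withdrawal assessment in Section 8.2 already collects a mucositis score.
3. **Section 10.1.1.** Replace the sentences on possible significance and accurate powering with the expected precision of the chosen measure. If it is a mean difference, that is about +/-0.89 SD at 11 per arm, or +/-0.75 SD at 15.

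The cost is protocol/SAP wording and a few tables, with no new data collected. The downside is that one scale must be ranked first and the sizing claim becomes less favourable.
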